### **Visit 3: 6 Month Follow-up**

- Attend fasting
- Routine clinical examination including measurement of height, weight, waist circumference, hip circumference
- Measurement of blood pressure and heart rate
- 15mL (approximately 3 tablespoons) of venous blood taken for glucose, HbA1c, lipids, Creatinine, ALT, AST, GGT, insulin, cardiovascular biomarkers and serum save
- Urine pregnancy test in female subjects of childbearing age
- Random urine sample for microalbumin:creatinine ratio
- EQ-5D, RPAQ, TTM, food frequency and acceptability questionnaires completed
- Actigraph physical activity monitor fitted according to manufacturer's instructions and worn for 7 days. Pre-paid addressed envelopes will be provided for the return of the Actigraph device or subjects may return them to the clinic.

### **Visit 4: 12 Month Follow-up**

- Attend fasting
- Routine clinical examination including measurement of height, weight, waist circumference, hip circumference
- Measurement of blood pressure and heart rate
- 15mL (approximately 3 tablespoons) of venous blood taken for glucose, HbA1c, lipids, Creatinine, ALT, AST, GGT, insulin, cardiovascular biomarkers and serum save
- Urine pregnancy test in female subjects of childbearing age
- Random urine sample for microalbumin:creatinine ratio
- EQ-5D, RPAQ, TTM, food frequency and acceptability questionnaires completed
- Actigraph physical activity monitor fitted according to manufacturer's instructions and worn for 7 days. Pre-paid addressed envelopes will be provided for the return of the Actigraph device or subjects may return them to the clinic.

### **Visit 5: 24 Month Follow-up**

- Attend fasting
- Routine clinical examination including measurement of height, weight, waist circumference, hip circumference
- Measurement of blood pressure and heart rate
- 15mL (approximately 3 tablespoons) of venous blood taken for glucose, HbA1c, lipids, Creatinine, ALT, AST, GGT, insulin, cardiovascular biomarkers and serum save
- Urine pregnancy test in female subjects of childbearing age
- Random urine sample for microalbumin:creatinine ratio
- EQ-5D, RPAQ, TTM, food frequency and acceptability questionnaires completed

- Actigraph physical activity monitor fitted according to manufacturer's instructions and worn for 7 days. Pre-paid addressed envelopes will be provided for the return of the Actigraph device or subjects may return them to the clinic.

**Data** During the course of the study visits some data will be stored on laptop computers, not connected to the internet, for later statistical analysis. These data will be coded and non identifiable. Participant data will be stored in a locked filing cabinet in a secure room in Imperial College Healthcare NHS Trust. Only the research team (clinical research fellow and research nurse) will have access to the filing cabinet. Electronic data will be stored by subject number only on NHS desktop computers which are in the same locked room. At the end of each visit the anonymised data will be transferred immediately to the secure NHS computers and will be deleted from the laptop. Access to NHS computers is only by members of NHS staff with appropriate login privileges.

All data will be stored in an anonymised form by using study numbers for identification of participants. The NHS code of confidentiality will be followed and all activity will meet the requirements of the data protection act.

Only members of the clinical research team and those responsible for direct care will have access to subjects' data during the study. The data generated by the study will be analysed by the research team from Imperial College. The analysis will be on anonymised data and will take place in Imperial College Healthcare NHS Trust and in Imperial College academic buildings in the Faculty of Medicine.

**Subject inclusion criteria** Subjects may be recruited if:

Adults 18 yrs or over and less than 75 yrs

HbA1c between 6.0-6.4% (42-47 mmol/mol)

(HbA1c test performed within a week before full screening date can be used for inclusion criteria.)

**Subject exclusion criteria** Subjects are excluded if:

FPG equal or greater than 7.0 mmol/l

Pregnant or planning pregnancy

Breastfeeding

Enrolled in other clinical trials

Have active malignancy or under investigation for malignancy

Are unable to follow the protocol for any other reason

**Subject withdrawal criteria** Subjects will be withdrawn from the study in the case of:

1. Loss of capacity to give informed consent
2. Terminal illness
3. Diagnosis of type 2 diabetes by any validated criteria in any care setting (see **Efficacy** for more details)

Withdrawal will be immediate and subjects will be followed up in the appropriate care setting.

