**Trial Design** Subjects with impaired glucose regulation (defined as an HbA1c of 6.0-6.4%) will be randomised to usual care or usual care with text messaging. Text messages will be delivered three times weekly and will contain educational, motivational and supportive content on diet, physical activity, lifestyle and smoking. The content will be appropriate to the stage of the transtheoretical model of behavioural change that the subject is in (see appendices for transtheoretical model questionnaire, assessment scale and text messages). The primary outcome is progression to type 2 diabetes as defined by an HbA1c of 6.5% or over. Secondary outcomes are:

- Change in physical activity as measured by Actigraph and Recent Physical Activity Questionnaire (RPAQ)
- Change in weight, BMI, waist circumference, hip circumference and waist:hip ratio
- Change in fasting plasma glucose and HbA1c
- Change in lipid profile (total cholesterol, triglycerides, LDL cholesterol and HDL cholesterol)
- Liver function as measured by alanine transaminase (ALT), aspartate transaminase (AST) and gamma-glutamyl transferase (GGT)
- Change in diet assessed by validated food frequency questionnaire
- Quality of life assessed by EQ-5D questionnaire
- Acceptability of text message intervention assessed by questionnaire
- Cardiovascular biomarkers including hsCRP, adiponectin, PAI (plasminogen activator inhibitor), uric acid, white cell count, albumin, IL-6, IL-1, TNF- $\alpha$ , monocytes chemotactic protein-1, leptin, resistin, endothelin-1, E-selectin, soluble vascular cellular adhesion molecule-1 (sVCAM-1) and soluble interstitial cellular adhesion molecule-1 (sICAM-1)
- Insulin secretion and sensitivity

Lifestyle modification targets in the study are in line with previously published type 2 diabetes prevention studies:

1. A minimum of 150 minutes moderate intensity exercise per week
2. A minimum of 7% weight loss or achievement of a BMI of 25kg/m^2 (23kg/m^2 in South Asian subjects)
3. Less than 30% of total Kcal intake from fat
4. Less than 10% of total Kcal intake from saturated fat
5. Greater than 15g fibre per 1000Kcal intake

[figure not shown]
**Methodology** Randomised, controlled trial.

**Timescale** It is anticipated that the study will take 3 years with each subject being enrolled for 2 years with a total of 5 visits in that period.

**Population** n=2268 across the UK and India. n=1134 in UK sites randomized equally to 2 groups of 567.

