Recruitment will be undertaken in both primary and secondary care targeting people with impaired glucose regulation (IGR). Identifying this group of people will be done by searching existing pathology databases held in NHS laboratories or GP records for fasting plasma glucose, HbA1c or an oral glucose tolerance test. These glycaemic measurements are done as part of the NHS Health check programme or other routine screening and are performed in NHS hospital labs. Access to the record of laboratory results will be done by only authorised personnel in the pathology department. Potential participants meeting the inclusion criteria for the study will be sent letters of invitation by the study team. Existing samples will not be used in the study. In addition, adverts and face to face talks to potential participants can be used where appropriate. An invitation letter and a participant information sheet together with a reply slip will be sent to potential participants. Those who have shown interest in the reply slips are encouraged to ask questions about the study. Only those who have agreed to take

part will be invited for screening. Informed consent will be taken before conducting any study procedures. During screening, glycaemic status will be confirmed with an HbA1c.

No concomitant medical therapies are contra-indicated. All study visits will take place in a local clinic at one of NHS research collaborating sites for the study.

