### Visit 1: Screening

- Attend fasting
- Routine clinical examination including measurement of height, weight, waist circumference, hip circumference
- Measurement of blood pressure and heart rate
- 15mL (approximately 3 tablespoons) of venous blood taken for glucose, HbA1c, lipids, Creatinine, ALT, AST, GGT, insulin, cardiovascular biomarkers and serum save
- Urine pregnancy test in female subjects of childbearing age
- Random urine sample for microalbumin:creatinine ratio
- EQ-5D, RPAQ, TTM and food frequency questionnaires completed
- Actigraph physical activity monitor fitted according to manufacturer's instructions and worn for 7 days. Pre-paid addressed envelopes will be provided for the return of the Actigraph device or subjects may return them to the clinic.

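### Previously diagnosed or drug-treated diabetes is not an exclusion, although that diagnosis is both a withdrawal reason and a primary event; the governing HbA1c at screening is also left open

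*Protocol*

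**What the plan says.** **Entry.** Trial Design defines the target condition by a number alone: "Subjects with impaired glucose regulation (defined as an HbA1c of 6.0-6.4%) will be randomised". Subject inclusion criteria repeat that range, with an age limit, and add that an "HbA1c test performed within a week before full screening date can be used for inclusion criteria". The only glycaemic item under Subject exclusion criteria is "FPG equal or greater than 7.0 mmol/l". The others concern pregnancy or planned pregnancy, breastfeeding, other trials, malignancy and inability to follow the protocol. The recruitment text under Population says "No concomitant medical therapies are contra-indicated".

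**Screening.** The recruitment text also says "During screening, glycaemic status will be confirmed with an HbA1c". Visit 1 includes "venous blood taken for glucose, HbA1c, lipids, Creatinine, ALT, AST, GGT, insulin, cardiovascular biomarkers and serum save".

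**Withdrawal and outcome.** Subject withdrawal criteria list "Diagnosis of type 2 diabetes by any validated criteria in any care setting". Efficacy counts as primary events diabetes found by FPG or HbA1c at visits 3, 4 and 5, and diabetes diagnosed by validated criteria elsewhere. For a participant without symptoms, Efficacy requires a raised result to be repeated after 4 weeks and to be raised again.

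**The concern.** An incidence endpoint needs a population free of the event at entry. Here the same status, a diagnosis of diabetes made anywhere by accepted criteria, ends participation and counts as the outcome but does not bar entry. Two kinds of people can pass the criteria as written:

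- someone with diagnosed diabetes whose treatment or lifestyle holds HbA1c at 42-47 and FPG below 7.0;
- someone with a diabetic glucose tolerance test on record whose HbA1c and FPG lie in the permitted range.

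Neither can progress to diabetes. Counted as events, they add the same amount to both arms and pull the risk ratio towards 1. Kept below threshold by drugs, they count as non-events and lower the apparent incidence. Recruitment makes the route plausible: it covers primary and secondary care and searches pathology databases and GP records for FPG, HbA1c or glucose tolerance results. No step checks for an earlier diagnosis.

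A smaller question concerns screening. If a test from the preceding week qualifies a person and the visit 1 sample is 48 or over, the protocol gives no rule for that disagreement.

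**Working it through.** No stated figure is in dispute. The sample size adds up (2 × 567 = 1134 for the UK; 2 × 1134 = 2268 overall). The protocol gives no event rates, power or significance level, so the numbers in steps 2 and 3 are illustrations under assumptions.

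**Step 1. The definitions side by side**

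| Status at screening | Bars entry? | Withdrawal reason? | Primary event? |
|---|---|---|---|
| FPG 7.0 or over | Yes | If diagnosed | Yes, with repeat if no symptoms |
| HbA1c 48 or over on the qualifying test | Yes, outside 42-47 | If diagnosed | Yes, with repeat if no symptoms |
| HbA1c 48 or over at visit 1 after a qualifying earlier test | Not stated | If diagnosed | Not on one result without symptoms, under Efficacy |
| Diabetes diagnosed earlier, results now in range | No | Yes | Diagnosis elsewhere counts |
| On glucose-lowering drugs, results in range | No | If diagnosed | If diagnosed |

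The fourth and fifth rows are the main defect; the third is the secondary one.

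**Step 2. What a fraction *f* of prevalent cases would do**

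Assumed: true 2-year risks of 20% and 14%, 567 per arm (the UK allocation), two-sided 5% test, the same *f* in both arms.

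Counted as events, each observed risk is *f* + (1 − *f*)*p*. At *f* = 0.05 this is 0.05 + 0.95 × 0.20 = 0.240 and 0.05 + 0.95 × 0.14 = 0.183, a ratio of 0.763. Power is Φ{[*d* − 1.96√(2p̄(1 − p̄)/*n*)] / √([p₁(1 − p₁) + p₂(1 − p₂)]/*n*)}, where *d* = p₁ − p₂.

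| *f* | Observed risks | Risk ratio | Power |
|---|---|---|---|
| 0 | 0.200, 0.140 | 0.70 | 77% |
| 0.02 | 0.216, 0.157 | 0.73 | 72% |
| 0.05 | 0.240, 0.183 | 0.76 | 65% |
| 0.10 | 0.280, 0.226 | 0.81 | 55% |

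Counted as non-events, each observed risk is (1 − *f*)*p*. At *f* = 0.10 the risks are 0.180 and 0.126. The ratio stays at 0.70, the difference falls from 0.060 to 0.054, and both incidences are understated by a tenth. The values of *f* are arbitrary; the document gives no basis for choosing among them.

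**Step 3. Disagreement between two HbA1c tests**

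Assumed: true HbA1c normal with mean 5.9% and SD 0.35; independent readings rounded to one decimal; first reading 6.0-6.4%; within-person SD 0.10, 0.15 or 0.20.

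| Later readings | SD 0.10 | SD 0.15 | SD 0.20 |
|---|---|---|---|
| Visit 1 at 6.5 or over | 5% | 8% | 11% |
| Visit 1 and a repeat both 6.5 or over | 2.1% | 2.9% | 3.8% |
| Visit 1 below 6.0 | 16% | 24% | 30% |

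The middle row applies the Efficacy repeat rule. With an assumed mean of 5.7% it falls to about 1-2%. The bottom row matters for the fix: if visit 1 had to fall in the full entry range again, about 21% (5 + 16) to 41% (11 + 30) of those qualifying on the earlier test would fail.

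**The case against.** The protocol plainly intends a population without diabetes. It speaks of people at risk, recruits largely through Health Checks and routine screening, and would withdraw anyone who holds the diagnosis. Sites would probably turn known cases away. The qualifying HbA1c and FPG must also lie below both biochemical thresholds of the endpoint.

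The last point stands in full. A reader might infer that entry imposes no freedom from the endpoint at all; that goes too far, because the gap is confined to diagnoses and treatment not visible in the two qualifying results. The appeal to intention is weaker. Trial Design makes the HbA1c range the definition of impaired glucose regulation, so the label does not exclude a treated patient within the range, and a withdrawal rule acts after entry.

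A reader might also infer that the one-week allowance lets a visit 1 value of 48 or over be overridden. The text does not say so. It lets the earlier test be used, and elsewhere has glycaemic status confirmed by HbA1c during screening. Nor does one such value establish the event in a person without symptoms, since Efficacy asks for a repeat. (Trial Design states the 6.5% threshold without one, which is a separate inconsistency.) Multiplying the single-reading 5-11% by 1134 to obtain a headcount would therefore be unsound: it ignores the repeat rule and supposes that everyone used the earlier test and that sites disregarded visit 1.

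**Conclusion.** The main point holds on the text. Following the criteria exactly can enrol people who already have the diagnosis that the trial treats as its outcome and as a reason for withdrawal. On average 1:1 randomisation spreads them equally, so the document does not support a claim of bias between arms. The expected harm is dilution where they are counted as events, and mis-stated incidence in either case. The number of such people cannot be estimated from the protocol; step 2 shows only how the effect would scale under assumed risks.

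The secondary point is an ambiguity, not a permissive rule. The protocol does not say which HbA1c governs when the two disagree, and a value of 48 or over is not listed as an exclusion. Under the assumed distributions, about 1-4% of those qualifying on an earlier test would be confirmed at 48 or over; the share of all participants would be lower if only some used that test.

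**What to change.** 1. Add to Subject exclusion criteria any previous diagnosis of diabetes, by any validated criteria in any setting, and current use of glucose-lowering medication. Entry then matches the withdrawal and outcome definitions. The cost is two lines in an amendment, a history and medication check at screening, and a few more screen failures.

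2. Reconcile the recruitment text, Visit 1 and Subject inclusion criteria by stating which HbA1c governs. A visit 1 result in the diabetic range should be resolved under the repeat rule already in Efficacy before the person is randomised. The cost is a delay of about 4 weeks for those affected.

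3. Do not require visit 1 to fall in the full 42-47 range a second time. On the assumptions in step 3 that would lose 21-41% of people qualifying on the earlier test, mostly because of readings below 6.0%, which have nothing to do with already having the endpoint.

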### **Efficacy**

The primary outcome will be progression to type 2 diabetes as measured by FPG (Fasting Plasma Glucose) or HbA1c at visits 3, 4 and 5 or by any validated criteria in any other care setting. The WHO/IDF criteria for diagnosis of diabetes will be used throughout.

1. If participant presents symptoms of diabetes and, FPG (Fasting Plasma Glucose)  $\geq 7.0$  OR HbA1c  $\geq 48$  then no repeat test is needed. The participant is diabetic.
2. If the participant does not present symptoms of diabetes;
  - If FPG  $\geq 7.0$  and HbA1c  $\geq 48$  then repeat both tests after 4 weeks. If the repeat results are FPG  $\geq 7.0$  or / and HbA1c  $\geq 48$ , the participant is diabetic.
  - If FPG  $< 7.0$  and HbA1c  $\geq 48$  then repeat HbA1c after 4 weeks. If the second result is  $\geq 48$ , the participant is diabetic.
  - If FPG  $\geq 7.0$  and HbA1c  $< 48$  then repeat FPG after 4 weeks. If the second result is  $\geq 7.0$ , the participant is diabetes.

Secondary outcomes will be:

- Change in physical activity as measured by Actigraph and Recent Physical Activity Questionnaire (RPAQ)
- Change in weight, BMI, waist circumference, hip circumference and waist:hip ratio
- Change in fasting plasma glucose and HbA1c
- Change in lipid profile
- Liver function as measured by alanine transaminase (ALT), aspartate transaminase (AST) and gamma-glutamyl transferase (GGT)
- Change in diet assessed by validated food frequency questionnaire
- Quality of life assessed by EQ-5D questionnaire
- Cardiovascular biomarkers including hsCRP, adiponectin, PAI (plasminogen activator inhibitor), uric acid, white cell count, albumin, IL-6, IL-1, TNF- $\alpha$ , monocytes chemotactic protein-1, leptin, resistin, endothelin-1, E-selectin, soluble vascular cellular adhesion molecule-1 (sVCAM-1) and soluble interstitial cellular adhesion molecule-1 (sICAM-1)
- Insulin secretion and sensitivity as calculated from fasting plasma glucose and insulin measurements

**Safety** Adverse events will be reported to the REC, the sponsor and the Principal Investigator immediately. Subjects will be followed-up after one week following an adverse event and thereafter in the clinically indicated follow up setting.

**Statistics** Missing, unused, and spurious data will be assessed on an individual basis and may be ignored, withdrawn or the visit may be removed from the analysis with appropriate justification adjudicated by the Principal Investigator.

**Direct Access to Source Data/Documents** The investigator(s)/institution(s) will permit trial-related monitoring, audits, IRB/IEC review, and regulatory inspection(s), providing direct access to source data/documents.

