**Study Management** The day-to-day management of the study will be co-ordinated by [name]. Weekly research meetings and monthly data reviews will be chaired by the chief investigator or other senior researcher. Annual reports to the funder and sponsor will be written and submitted. A data monitoring committee will be convened including a lay member with diabetes and appropriate experts not involved with the study.

**Publication Policy** The study will be registered on the clinicaltrials.gov system and results will be disseminated by peer reviewed scientific journals, internal report, conference presentation and publication on websites. No identifiable personal data will be published. All anthropometry and personal clinical data will be expressed as mean/ median and spread of the population in the study. All participants will be informed of the results by letter at the conclusion of the study and details of any publications that arise from the study will be disseminated to participants.

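### The protocol lets the Principal Investigator drop doubtful data or whole visits case by case, without criteria and without masking to arm or result, which permits biased exclusion of primary events

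*Protocol*

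**What the plan says.** The rule is in the Statistics paragraph at the end of the Efficacy section. Its scope is: "Missing, unused, and spurious data will be assessed on an individual basis". Its consequence is that such data "may be ignored, withdrawn or the visit may be removed from the analysis with appropriate justification adjudicated by the Principal Investigator". This is the protocol's only text on handling missing or doubtful data.

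Four other places bear on it:

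- **Comparison** (Trial Design): subjects "will be randomised to usual care or usual care with text messaging". No sham messages are described, and no masking of investigator, assessor or analyst.
- **Primary outcome** (Efficacy): "progression to type 2 diabetes as measured by FPG (Fasting Plasma Glucose) or HbA1c at visits 3, 4 and 5", or a diagnosis by validated criteria in another care setting.
- **Who analyses** (Data paragraph after Visit 5): "The data generated by the study will be analysed by the research team from Imperial College". The same paragraph says: "All data will be stored in an anonymised form by using study numbers for identification of participants".
- **Oversight** (Study Management): "A data monitoring committee will be convened including a lay member with diabetes and appropriate experts not involved with the study". No role in data exclusions is given to it.

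**The concern.** This is a rule that the protocol states, not a detail it leaves to the analysis plan. It combines three things: a category that is not defined (spurious), a remedy that can delete a whole visit, and a single decision-maker from inside the trial who also judges whether the justification is adequate. Nothing in the text keeps arm or result from that person.

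Because the primary outcome is read largely from the visit data, removing a visit can remove a primary event. If removals depended even modestly on arm, the comparison would no longer be the randomised one, and the nominal significance level would not hold. The loss may also be permanent: under the withdrawal criteria a participant diagnosed with diabetes leaves the study at once, so no later study visit would supply the event again.

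**Working it through.** **Reading the passages together.**

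1. *Can arm be known?* Participants know whether they receive messages. The acceptability questionnaire is completed at visits 3, 4 and 5, the same visits that supply glucose and HbA1c. The protocol never uses the term open-label, so that label is an inference. What can be said is that no masking of the decision-maker is described.
2. *Can the result be known?* The rule does not say that decisions are made without the result or before the data are seen, and it sets no time limit such as database lock.
3. *Does another provision close the gap?* Storing data by study number hides identity, not arm or outcome. Access to source data for monitoring and audit would let an exclusion be traced afterwards, but sets no criteria for making it. The data monitoring committee has no stated part in exclusions.

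**Illustration of scale.** The protocol attaches no figure to this rule, and it states no alpha, power, event rate or effect size, so there is no plan figure to reproduce beyond the totals: 2 × 567 = 1134 and 2 × 1134 = 2268, which agree.

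Inputs:
- From the protocol (Population): 567 per arm in the UK; 2268 overall, hence 1134 per arm if India is also allocated 1:1 (equal groups are stated for the UK only).
- Assumed, not in the protocol: two-sided alpha 0.05; no true effect; incidence p = 0.10, 0.20 or 0.30; a share q of events discounted in one arm only, with those participants then counted as event-free.

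Let p₂ = p(1 − q), d = p − p₂ and p̄ = (p + p₂)/2. Then

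SE₀ = √[2p̄(1 − p̄)/n], SE₁ = √[(p(1 − p) + p₂(1 − p₂))/n],

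P(reject) = Φ[(d − 1.96·SE₀)/SE₁] + Φ[(−d − 1.96·SE₀)/SE₁].

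Example with n = 567, p = 0.20, q = 0.10 (about 11 of 113 events): p₂ = 0.18, d = 0.02, p̄ = 0.19, SE₀ = 0.0233, SE₁ = 0.0233. The two terms are 0.135 and 0.002, so P(reject) = 0.138 instead of 0.05.

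| Share of one arm's events dropped | n per arm | p = 0.10 | p = 0.20 | p = 0.30 |
|---|---|---|---|---|
| 5% | 567 | 0.059 | 0.071 | 0.086 |
| 5% | 1134 | 0.069 | 0.092 | 0.123 |
| 10% | 567 | 0.089 | 0.138 | 0.201 |
| 10% | 1134 | 0.128 | 0.229 | 0.353 |

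**Sensitivity to the denominator.** If the affected participants leave the analysis altogether, then p₂ = p(1 − q)/(1 − pq) and that arm has n(1 − pq) participants. For the example, p₂ = 0.18/0.98 = 0.184 with 567 × 0.98 = 555.7 participants, and the same test with unequal arm sizes gives 0.107 rather than 0.138. Over 10% to 30% incidence, dropping 10% then gives 0.081 to 0.125 at 567 per arm and 0.114 to 0.204 at 1134; dropping 5% gives 0.058 to 0.068 and 0.065 to 0.086. The inflation is smaller but remains.

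**Number of decisions involved.** With 567 per arm and 113 events in one arm, the pooled two-proportion test gives p = 0.089 against 91 events and p = 0.043 against 87. Four further exclusions separate the two results.

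**The case against.** The best defence is that the sentence is ordinary data-cleaning language. It says *may*, it is limited to missing, unused and spurious data, and it asks for a justification. Several provisions make abuse harder:

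- Without symptoms, an event needs a confirmatory repeat after 4 weeks, and a confirmed pair of results is hard to call spurious.
- Diagnoses made in other care settings also count, and a diagnosis leaves a record outside the study visits.
- Source data are open to audit.
- The Consent section keeps participants given alternative treatment in the follow-up and the data analysis.

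All of this stands, and it limits how far the rule could be stretched. It does not supply criteria or masking. The repeat test governs whether an event is real, not which visits enter the analysis.

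Some stronger readings are tempting but are not supported:

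- *That the rule is biased in itself.* It permits biased handling; it does not prescribe it.
- *That any event is a surprising value and so open to deletion.* Entry HbA1c is 6.0–6.4% and the threshold is 6.5%, so a crossing is not anomalous.
- *That the monthly reviews expose results by arm.* The text says only: "Weekly research meetings and monthly data reviews will be chaired by the chief investigator or other senior researcher". It does not say what data are shown.
- *That no analysis plan could repair this.* A plan could narrow a permissive sentence with criteria and masked review without contradicting it. The plan is not at hand, so its content cannot be judged.

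**Conclusion.** The point holds as a defect in a rule the protocol states: exclusion of data or visits is left to one person's case-by-case judgement, with no objective criteria and no requirement to decide without sight of arm or result, in a trial whose participants cannot be masked and whose primary events come largely from the visits concerned. It permits exclusions informed by arm and outcome. Nothing shows that such exclusions were intended or took place.

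The size is conditional. The tabulated range, from 0.059 to 0.353, rests on assumed incidence and alpha and on every removal falling in one arm. Equal proportionate removal from both arms would leave the two event rates equal under no effect and the type I error near 0.05. The figures show how sensitive the comparison is to a few one-sided decisions; they do not estimate a bias in this trial.

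**What to change.** Replace the sentence in the Statistics paragraph with a rule that says:

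1. All randomised participants are analysed in the arm to which they were allocated.
2. A recorded result is removed only for a documented laboratory, sample or identity error.
3. The decision is made from a listing that shows neither arm nor outcome status, and is logged with its reason before database lock.
4. Exclusions are reported by arm.
5. A sensitivity analysis restores every recorded value.

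The method for missing outcomes can stay with the analysis plan. The cost is protocol wording and a masked listing; sample size, visits and participant burden do not change.
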